#### 9.3.2 Correlation of Efficacy Endpoints

The potential covariates in this study are listed in Section 8.2. A 2x2 correlation analysis will be performed on all combinations to evaluate the relationship between the covariates. The Pearson Correlation Coefficient will be used to measure the association between age as a continuous variable and the NVIQ/DQ score as described in Section 9.2. If the coefficient is <.5, we will assume little to no association. The Point-Biserial Correlation Coefficient will also be used to measure the association between combinations of continuous and binary variables such as NVIQ/DQ and ASD diagnosis, respectively. The binary variables will be assigned a numeric value of 1 or 2. The Pearson Chi-Square test will be used to measure the association between combinations of categorical variables such as age group and genotype or sex and history of regression. A p-value < 0.10 would indicate association between the variables.

The correlation analysis may inform the selection of covariates (or combinations thereof) to be used in a linear regression analysis on all pre-specified endpoints. Endpoints of interest for the linear regression analysis will be:

- CGI-I Overall Score
- Caregiver Impression of Change Overall Score
- CGI-S Overall Score
- ORCA t-score
- BPI-SF Total frequency and severity scores
- ABC-2 Total Score
- CSHQ Total Score
- GIHQ Total frequency, relevancy, and importance Scores
- Vineland ABC score
- Vineland GSV, raw, and standard domain scores
- QI-Disability Overall Score
- ICND Score

A multiple linear regression model will be determined using the forward selection method where covariates meeting the entry criterion (p-value <0.2) enter into the model. The final model will include all parameters that have successfully been entered into the model.

Addendum to the Final Statistical Analysis Plan

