11.3 Efficacy Analysis

Efficacy will be assessed by looking at within-participant changes from the Baseline period to the EOT using the efficacy endpoints listed in Section 6.3.2.

The participant's baseline characteristics and symptom severity will be established based on assessments collected during the 4 to 6 week Screening/Baseline period. Baseline values will be based on the average values of visits 1, 2, and 3 for assessments collected at more than one visit. A Wilcoxon signed rank test will be used to test for improvement and an exact significance level will be computed.

Potentially influential factors will be considered and addressed with a linear regression model. This model may include covariates such as age, sex, nonverbal NVIQ or NVIQ equivalent, genotype, history of regression (yes/no), ASD diagnosis (yes/no) with no more than two covariates included in any model. Descriptive statistics and corresponding graphics will be used to present the results. The safety and efficacy analysis details will be specified in the SAP.

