## 8.2 Adjustments for Covariates

A list of potential covariates to be used in descriptive summaries or analyses are provided below.

- Age at Baseline
- Sex (Male, Female)
- SB5 NVIQ or BSID-4 NVDQ at Baseline
- History of developmental regression (yes, no)
- ASD diagnosis (yes, no)
- CGI-S Overall Score at Baseline

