## 9.3.2 Correlation of Efficacy Endpoints

The potential covariates in this study are listed in Section 8.2. A 2x2 correlation analysis will be performed on all combinations to evaluate the relationship between the covariates. The Pearson Correlation Coefficient will be used to measure the association between age as a continuous variable and the SB5 NVIQ or BSID-4 NVDQ as described in Section 9.2. If the coefficient is <.5, we will assume little to no association. The Point-Biserial Correlation Coefficient will also be used to measure the association between combinations of continuous and binary variables such as SB5 NVIQ/BSID-4 NVDQ and ASD diagnosis, respectively. The binary variables will be assigned a numeric value of 1 or 2. The Pearson Chi-Square test will be used to measure the association between combinations of categorical variables such as age group and genotype or sex and history of regression. A p-value < 0.10 would indicate association between the variables.

The correlation analysis will support the selection of covariates (or combinations thereof) to be used in a linear regression analysis on all pre-specified endpoints. Endpoints of interest will be:

- CGI-I Overall Score
- CGI-S Overall Score
- ORCA t-score
- BPI-SF Total score
- ABC-2 Total Score
- CSHQ Total Score
- GIHQ Total Score
- Vineland ABC score
- Vineland GSV, raw, and standard domain scores
- QI-Disability Overall Score
- ICND Score

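### The correlation cut-off in SAP and Addendum 9.3.2 ignores the sign of r, and the Addendum's forward selection has no two-covariate limit although the protocol sets one

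*SAP*

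**What the plan says.** **Correlation screen.** SAP 9.3.2 and Addendum 9.3.2 use Pearson's r for continuous age against non-verbal IQ or DQ. Both give the same rule: "If the coefficient is <.5, we will assume little to no association". Neither has a separate rule for negative values.

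**Use of the screen.** The SAP has it support covariate choice. The Addendum is weaker: "The correlation analysis may inform the selection of covariates (or combinations thereof").

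**Model building.** SAP 9.3.2 has no selection rule. The Addendum adds forward selection in which "covariates meeting the entry criterion (p-value <0.2) enter into the model", and then: "The final model will include all parameters that have successfully been entered into the model". No maximum is given. SAP 8.2 lists six candidates: age, sex, "SB5 NVIQ or BSID-4 NVDQ at Baseline", history of regression, ASD diagnosis and baseline CGI-S.

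**Protocol.** Section 11.3 and the synopsis describe the linear regression "with no more than two covariates included in any model".

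**Precedence.** SAP 2 (Introduction) says that the SAP is read together with the protocol and prevails where the two disagree.

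**The concern.** These are two separate wording errors in one section.

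1. A cut-off meant to describe strength of association is written on the signed coefficient. Every r from -1 to just under +0.5 gets the same label. The pair it applies to is one where a negative value is built in for children on the BSID-4, because Addendum 9.2.16 divides the age equivalent by chronological age. The SB5 z-deviation score is derived by age at assessment and lacks this feature. At stake is a report that tells the reader age and DQ are essentially unrelated when they are strongly related.

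2. The Addendum is the first text whose rule can produce a model with more than two covariates. It neither mentions nor withdraws the protocol limit. If the precedence clause applies, the limit lapses with no reason given. A three-covariate model would then follow the SAP, so the SAP's requirement to document deviations from itself would not bring it to light. Protocol 6.2.2 names the influence of baseline attributes on response as something the study should learn about, and this section is where that is analysed.

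**Working it through.** The plan gives no figure of its own here, so there is nothing to reproduce.

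**1. Signed cut-off**

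*Logic.* With t = r·√[(n − 2)/(1 − r²)] and r = -0.8:
- n = 10: t = -0.8·√(8/0.36) = -3.77, p = 0.005.
- n = 20: t = -0.8·√(18/0.36) = -5.66, p = 0.00002.

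The rule as written still puts both below the cut-off.

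*Why negative is expected.* Non-verbal DQ = age equivalent / chronological age × 100. For an assumed age equivalent of 18 months, DQ is 18/48 × 100 = 37.5 at age 4 and 18/192 × 100 = 9.4 at age 16.

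*How often r ≤ -0.5.* From the documents: ages 3-17 and 10-20 participants (SAP 2.2), and mental ages of 3.5-36 months (Protocol 5.1). Assumed: uniform age, and the distribution and slope of age equivalents. There were 20,000 samples per case for the cases reported in full. Sample sizes were 10, 16 and 20, or 10, 15 and 20 in rows marked *. Age equivalents were held within 3.5-36 months. All children are on the BSID-4.

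| Age equivalent (months) | Median r | Share with r ≤ -0.5 |
|---|---|---|
| Unrelated to age, mean 15, SD 5* | -0.77 to -0.79 | 96-99% |
| Unrelated to age, uniform 3.5-36 | -0.65 to -0.67 | 80-88% |
| Mean rises 12 to 24, SD 7 | -0.55 to -0.56 | 59-62% |
| Mean rises 8 to 20, SD 5* | about -0.5 | 48-51% |
| Mean rises 8 to 28, SD 5* | -0.38 | 26-35% |
| Mean rises 8 to 30, SD 7 | about -0.30 | 17-27% |
| Mean rises 5 to 36, SD 7 | -0.02 to -0.05 | 3-10% |

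Some children may take the SB5. Take assumed SB5 scores with mean 45 and SD 10, unrelated to age, and three of the cases above (uniform, 12 to 24, 8 to 30):
- 20% on SB5: 43-48%, 17-29% and 6-16%.
- 40% on SB5: 21-31%, 8-18% and 3-11%.
- The assumed SB5 mean matters. At a mean of 20, the first 20% figure becomes 62-65%.

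The rule flags r ≥ +0.5 in at most 4.6% of samples in those three cases at any SB5 share, and in 2-10% under the steepest slope (5 to 36).

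**2. No maximum on covariates**

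*Degrees of freedom.* Residual df = n − 1 − k. At n = 10, six covariates leave 10 − 1 − 6 = 3 and two leave 10 − 1 − 2 = 7.

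*Chance of exceeding two on noise.* Treating six candidates as independent tests at 0.2:
- P(at least one) = 1 − 0.8⁶ = 73.8%.
- P(three or more) = 1 − (0.262 + 0.393 + 0.246) = 9.9%.

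Forward selection re-tests after each entry, so it was simulated: 10,000 noise datasets per sample size and setting, n = 10-20, no removal. Sex was set at 50% and baseline CGI-S at 4-7.
- ASD 50%, regression history 30%: three or more enter in 12-17% of models.
- ASD 90-95%, regression history 10%: 10-13%. Protocol 5.1 reports up to 95% above an ASD screener cut-off, which is not a diagnosis.
- The Addendum also mentions "categorical variables such as age group and genotype or sex and history of regression", although SAP 8.2 does not list genotype. With a two-level genotype as a seventh candidate: 18-23%.

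*Number of models.* The Addendum's endpoint list, leaving out Vineland GSV, raw and domain scores, gives CGI-I, Caregiver Impression of Change, CGI-S, ORCA, BPI-SF (2), ABC-2, CSHQ, GIHQ (3), Vineland composite, QI-Disability and ICND, which is 14. Expected models over the limit: 14 × 0.10 = 1.4 to 14 × 0.17 = 2.4.

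*Effect of the limit on false positives.* With six candidates, stopping at two terms lowers the noise-only rate of an overall F-test p < 0.05 from 28-36% to 26-33%, about 1-3 percentage points.

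**The case against.** **On the cut-off.** A threshold for weak association is naturally read as one of magnitude. The same paragraph uses point-biserial correlations with arbitrary 1/2 coding, where the sign means little. No passage excludes a covariate because of the label, and no output table for the label is described. The percentages rest almost wholly on assumed age-equivalent patterns and SB5 use, and a steep enough slope nearly removes the problem. All of this is fair, and it limits the consequence to a wrong description. It does not change what the text says, and the sentence was carried into the Addendum unchanged.

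**On the limit.** The SAP is to be read with the protocol, so silence could mean that the limit still stands. If the texts do conflict, the SAP's precedence clause settles it, and Protocol 11.3 leaves efficacy detail to the SAP. The SAP had already changed the candidate list, adding CGI-S and omitting genotype. The regressions are exploratory, tests are descriptive, and the limit barely moves the false-positive rate. These points hold on consequence. But an instruction to keep every term that enters, with no maximum, is hard to reconcile with a two-term limit, and a programmer would not apply a limit that the Addendum does not state.

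**Conclusion.** Both parts hold. As written, the cut-off puts any negative correlation, however strong, in the lowest class, for a pair where negative is the expected direction on the BSID-4. As written, the selection rule can produce models that the protocol does not allow.

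The text facts are certain; the frequencies are not. The share of samples affected by the sign error ranges from about 3% to 99%, because the documents give neither the trend of age equivalents with age nor the share of children on the SB5. The rate of models above two covariates is firmer, at about 10-17% on noise with six candidates.

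The consequence is limited to exploratory description and to agreement between protocol and SAP. The correction should be made because it is nearly free, not because a main result depends on it.

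**What to change.** In SAP 9.3.2 and Addendum 9.3.2, write the cut-off as |r| < 0.5. In Addendum 9.3.2, stop forward selection at two covariates per model, in line with Protocol 11.3. If the sponsor means to drop the limit, the Addendum should say so and give the reason.

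The cost is a few words and a stop condition in the selection program. No new data are needed, and all six candidates can still be screened. The only loss is that each exploratory model can hold fewer covariates.

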The underlying neuropathology and severe neurological and neurodevelopmental impairments also lead to neurobehavioral dysfunction and dysregulation which substantially disrupt daily activities, put individuals at greater risk of harm, and can be potentially life-threatening. Hyperventilation and apnea result in a number of negative impacts on health including swollen abdomen, excessive burping, decreased oxygen saturation, changes in pallor, cyanosis, chronic hypoxia, and finger clubbing.^{6,9,10} Seizures can be debilitating to cognitive and neurological development. Self-injurious behaviors put individuals with PTHS at risk of physical harm, potentially with long-term cumulative effects which decreases overall quality of life. There is currently no on-going natural history study of PTHS. Cohort studies, and a recent consensus statement paper on diagnosis and treatment³ have provided detailed information characterizing the clinical manifestations of the disorder and their functional impact. This has provided insights on the symptoms that are central to the disorder and are important to patient functioning and well-being. The Pitt Hopkins Research Foundation (PHRF) maintains a family registry as part of the Coordination of Rare Diseases (CoRDS) Registry at Sanford which collects information on clinical symptoms (https://pitthopkins.org/research/how-to-get-involved-in-research-today/family-registry/). The PHRF also did an assessment of the patient and family experience by conducting a trend analysis of data shared through social networks.³⁴ In this analysis they identified the most concerning symptoms, most common methods of disease management, and unmet needs.

Together, the output from these initiatives and expert clinical advice has provided guidance into the important domain areas to address with NNZ-2591 treatment that would be most relevant and potentially beneficial to patients with PTHS (see Section 9.5.9). The secondary outcome of efficacy in this study will be assessed by evaluating a range of symptom areas to determine if there is preliminary evidence of efficacy, but also importantly to gather information about the performance of outcome measures and the influence of baseline patient attributes on clinical response.

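### Forward selection at p<0.2 from six candidates will often keep a covariate by chance, so entry into the final model is not in itself evidence of influence

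*SAP*

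**What the plan says.** Section 9.3.2 of the original SAP names endpoints for linear regression but gives no rule for choosing covariates. The addendum supplies one: "A multiple linear regression model will be determined using the forward selection method". A covariate comes in if its p-value is below 0.2. The next sentence keeps whatever enters: "The final model will include all parameters that have successfully been entered into the model".

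For candidates, the addendum refers to SAP Section 8.2, which opens: "A list of potential covariates to be used in descriptive summaries or analyses are provided below". Six follow: age, sex, SB5 NVIQ or BSID-4 NVDQ, history of developmental regression, ASD diagnosis and baseline CGI-S overall score. The addendum lets the correlation analysis guide which are used, but sets no rule for dropping any.

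Neither SAP document gives a removal criterion, shrinkage, a validation step or a correction for the search. SAP Section 8.5 plans no multiplicity adjustment. Protocol Section 11.3 limits each model to two covariates. The addendum is silent on that limit, and SAP Section 2 makes the SAP govern where the two are inconsistent.

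The purpose is stated in Protocol Section 6.2.2: besides preliminary efficacy, the study is to gather information on "the influence of baseline patient attributes on clinical response".

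**The concern.** An entry threshold of 0.2 accepts a one-in-five chance of admitting each irrelevant covariate, and the rule gives six of them a try. Once a covariate is in, nothing takes it out. Standard output from the selected model then computes p-values and R-squared as if the model had been fixed in advance.

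At stake is what the sponsor carries into later studies about which children respond. These regressions are the main planned model for that question, and SAP Section 8.3 plans no subgroup analyses. At this sample size a covariate picked up by chance can come with a small p-value and a large R-squared, and the plan gives the reader no way to see how much of that is due to the search.

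**Working it through.** The documents state no false-inclusion rate for this procedure, so there is no figure to reproduce.

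**Inputs from the documents**
- Entry threshold 0.2, all entered covariates kept (SAP addendum 9.3.2).
- Six candidates (SAP 8.2).
- 10 to 20 children (SAP 2.2).
- Two-sided tests (SAP 5).

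**Assumptions**
- The documents give no correlations among the covariates; latent correlations of 0 to 0.8 were tried.
- Mixed continuous, binary and ordinal covariates patterned on Section 8.2. The runs for final-model p-values and R-squared used age uniform over 3-17, half of each sex, regression 30%, ASD 60% and CGI-S 4-7. These proportions are illustrative.

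**Step 1. Chance that at least one covariate enters when none matters.** With independent candidates this is 1 − 0.8^k:
- k = 4: 1 − 0.8^4 = 0.59
- k = 5: 1 − 0.8^5 = 0.67
- k = 6: 1 − 0.8^6 = 0.738
- k = 7 (if genotype, named in Protocol 11.3, were added): 1 − 0.8^7 = 0.79

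Simulated forward selection with six candidates, 2,500 null data sets per cell:

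| n | correlation 0 | 0.3 | 0.5 | 0.8 |
|---|---|---|---|---|
| 10 | 0.740 | 0.713 | 0.655 | – |
| 12 | 0.725 | 0.698 | 0.670 | – |
| 16 | 0.735 | 0.712 | 0.662 | 0.530 |
| 20 | 0.734 | 0.702 | 0.657 | – |

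With independent covariates, 36-39% of null models keep two or more covariates and 13-17% keep three or more. The protocol's limit of two does not alter the chance of a first entry: with that limit, a separate run gave 0.73 at n=20 and 0.72 at n=10.

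**Step 2. Number of models affected.** The addendum lists 14 scores apart from the Vineland GSV, raw and domain scores, counting BPI-SF as two and GIHQ as three. If no covariate mattered for any of them, the expected number of models with an entered covariate is 14 × 0.738 ≈ 10, or 14 × 0.53 ≈ 7 at correlation 0.8.

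**Step 3. Final-model p-values and R-squared under no influence.** Across simulations at n = 10 to 20, 31-45% of final models show at least one covariate at p<0.05. One set of 1,500 replicates gave 33% at n=20 and 42% at n=10, with mean R-squared of 0.27 and 0.54 when something entered.

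The like-for-like comparator is any of six separate single-covariate tests at 0.05: 1 − 0.95^6 = 0.265, simulated at 25-32%. In that set, selection adds 33 − 26.5 ≈ 7 points at n=20 and 42 − 26.5 ≈ 16 points at n=10. Across runs the addition is roughly 5-17 points.

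**Step 4. One real covariate among six** (6,000 replicates, n=16, independent covariates):

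| correlation with outcome | real one enters | each null enters | share of entered covariates that are noise |
|---|---|---|---|
| 0.3 | 45% | 22% | 71% |
| 0.5 | 74% | 22% | 60% |
| 0.7 | 96% | 22% | 53% |

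For example, at 0.5 the five null covariates contribute 5 × 0.219 = 1.095 entries per model and the real one 0.742, so the noise share is 1.095/1.837 = 60%. Over n = 10, 16 and 20 with a real covariate at these strengths, the share ranges from 52% to 77%.

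**The case against.** The regression is exploratory and optional (SAP 9.2), tests are described as descriptive (SAP 5), and there is no primary efficacy endpoint (SAP 9.1). A liberal threshold in a hypothesis-generating step trades specificity for sensitivity, which is partly a matter of preference. That limits the consequence. It does not correct the estimates: an exploratory label does not tell a reader that p-values ignore a search.

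The 74% figure needs six nearly independent candidates, which is doubtful. The developmental quotient divides by chronological age (SAP addendum 9.2.16), so NVDQ is tied to age. With the mental ages of 3.5-36 months in Protocol 5.1 taken as uniform, their correlation is about −0.64. Protocol 5.1 also reports up to 95% above an autism screening cut-off, so ASD diagnosis may vary little. Allowing for both gives 67-70%. Hence a range, with 74% at its top.

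A reader might infer that the procedure cannot tell signal from noise. The documents do not support that. Step 4 shows a real covariate with correlation 0.5 entering about three times as often as a null one. A reader might also set the 31-45% against the 5% of one pre-specified test. That is unfair, because most of the excess comes from examining six covariates, which separate models would also do. Lastly, the addendum does not say that entered covariates will be called influential, or that p-values and R-squared will be tabulated; the word influential belongs to Protocol 11.3.

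**Conclusion.** The point stands in limited form. With no true influence, at least one covariate enters in about 74% of models if all six are offered and nearly independent, and in about 53% if correlations reach 0.8. Entry alone therefore does not show that an attribute matters: with one real covariate present, more than half of the entered covariates were noise in every scenario tried. Any p-values and R-squared reported from the selected model are too favourable, with selection itself adding roughly 5-17 points to the chance of a p<0.05 finding. The procedure still favours a strong real covariate. The sizes rest on the assumed covariate distributions and correlations.

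The change is worth making because it bears on a stated aim of the study. The consequence is confined to how covariate findings are interpreted. The addendum's silence on the protocol's two-covariate limit is a separate matter to reconcile; restoring that limit would not cure this problem.

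**What to change.** Replace the two forward-selection sentences in addendum 9.3.2 with fixed models, for instance: *For each listed endpoint, each covariate in Section 8.2 is fitted in a separate linear regression. The coefficient and 95% CI are reported for every covariate whatever its p-value, labelled exploratory and not adjusted for the examination of six covariates.*

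A two-covariate model named in advance, such as age with NVIQ/NVDQ, may be added because the two are mechanically related; it stays within the protocol's limit.

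If forward selection is kept, report one permutation p-value for the whole search in place of the unadjusted final-model p-values: permute outcomes across children, rerun the selection each time, and compare the largest test statistic with the observed one.

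The cost is addendum wording and a little programming. The downsides are no single final model per endpoint, less joint adjustment and slightly more output. Separate models do not remove the multiplicity of six covariates, but they show all six results with their imprecision and take selection out of the estimates.
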